10 DATA MANAGEMENT

10.1 Case Report Forms (CRFs)

For each subject enrolled who has given informed consent, completed the screening process, and began the study process, a CRF will be created and signed by PI or designee to certify completeness and correctness.

If a subject is withdrawn from the study due to a treatment-limiting adverse event, due diligence must be used to document the outcome. Source documentation verification will be performed by the study monitors. All CRFs will remain at the study site.

10.2 Data Handling

Data management based on GCP refers to the activities defined to achieve safe routines to enter clinical data information into a database, efficiently and avoiding errors. The data management routines include procedures for handling CRFs, database set-up and management, data entry and verification, data validation, and documentation of the performed activities including information of discrepancies in the process.

The database, the data entry screens, and program will be designed in accordance with the study protocol and the CRF. Single data entry and proofreading will be used for data entry and verification. Data validation will be performed after data entry and verification by manual review. When the clinical study coordinator has made all efforts to ensure that the data recorded in the CRFs and entered in the database is as correct and complete as possible, "clean file" is declared, and the database is closed. The clinical study coordinator should document the database closure in a signed written document. Final statistical analysis should be generated using data from the closed database. Any additional subsequent changes or corrections to the closed database should be documented in an audit trail.

11 STATISTICAL METHODS

11.1 Study Populations

The study population will include all subjects who are enrolled, and the entire study population will be included in statistical analyses.

11.2 Study Endpoints

The endpoint is a comparative analysis of pre and post-treatment photographs. Measurements and calculation will be performed based off of the portrait and profile images.

11.3 Analysis Method

The PI's study coordinator will perform all statistical analyses. This is in an effort to avoid any potential bias that could be created by the treating physician participating in the analysis. Given that there is inherent variability even in standardized portrait photography, the decision was made to perform measurements based on facial landmarks and distance ratios. Statistical analysis will be conducted using a paired *t* test.

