5 STUDY DESIGN

This is an open-label, prospective, postmarket study to assess the effect of premaxillary hyaluronic acid filler injection on nasal tip projection and upper lip position.

The study will enroll and treat a total of 20 subjects who are filler naïve and do not have any history of rhinoplasty, recent, 6 months upper lip augmentation, lip lift or other surgical procedures involving the upper lip, chin augmentation and orthognathic surgery. Patients in study are restricted from perioral neurotoxin or ablative resurfacing, facial cosmetic surgery, all subdermal directed aesthetic treatments or filler treatment other than which is dictated in the protocol during the course of the study.

Subjects, who fulfill all eligibility criteria, will undergo pre-treatment standardized 2D portrait photography. From the profile image, baseline nasal projection measurements will be documented according to Goode's ratio. Additionally, baseline upper lip position will be recorded by measuring the Z-angle, which is the intersection of the Frankfort horizontal line and the profile line as described by Merrifield. From the straight portrait image, the ratio of the upper lip vermilion height to the lower lip vermilion height will be documented. Subjects will then be injected with a maximum of 4 syringes of Restylane® Defyne to treat their premaxillary space per the discretion of the Principal Investigator (PI). If optimal correction result (OCR) has not been achieved additional touch-up injections of Restylane® Defyne may be injected 2 weeks post treatment visit to achieve OCR as per PI discretion.

Post OCR visits will be performed at 4 weeks following premaxillary injections. Subjects will be followed to assess any treatment-related adverse events (such as pain, nodules, swelling, redness, bruising, tenderness, itching, and headache) as well as pigmentation changes and/or keloid formation. Each subject will then be photographed with standardized photographs in a similar fashion as pre-treatment and the same measurements will be recorded.

Upon study culmination, pre-treatment and 1-month post OCR photographs will be assessed. Each patient will be evaluated to determine if nasal tip projection was increased causing an increase in upper lip projection. Additionally, the vermilion ratios will be compared to evaluate for change in upper lip vermilion height.

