8 STUDY PROCEDURES

8.1 Screening Visit

The PI and/or designee is responsible for keeping a record of all subjects screened for entry into the study and those subjects that were excluded, including exclusionary reason.

The following procedures will be performed:

1. The PI and/or designee is responsible to evaluate and confirm that a subject meets inclusionary/exclusionary criteria.
2. Subjects must provide signed informed consent with confirming signature from investigator/site designee.
3. Subject undergo standard 2D digital portrait photography.

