8.4. Visit 3: One Month Follow-up Visit

The following procedures will be performed:

1. Subject will undergo standardized 2D digital portrait photography.

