9 RESPONSE CRITERIA

9.1 Primary Variable Assessments

The primary assessment of this study is to determine the effect of premaxillary injection on nasal tip projection and upper lip projection for perioral rejuvenation. Efficacy of the injection on the subjects' 1-month post OCR with *Restylane® Defyne* will be done through comparative measurements taken on pre and post-treatment photographs.

Nasal tip projection will be assessed by Goode's ratio. The value is defined as nasal height over the nasal length. The nasal height is measured from the alar-facial groove to the tip-defining point and the nasal length is measured from the root of the nose, or nasion, to the tip-defining point. Upper lip projection will be measured by a method outlined by Merrifield in 1966. As described, a profile line is drawn tangent to the soft tissue chin and to the most anterior point of the upper lip. This line is then extended upward to the Frankfort horizontal plane. The angle at which these two lines intersect is called the Z angle. A change in the angle to a more acute value on postoperative photographs would indicate an increase in upper lip projection. This method was chosen because it is calculated independent of any postoperative nasal changes.

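### Nothing in the available text masks the person who measures the photographs to visit; section 11.3 only keeps the treating physician out of the analysis

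*Combined protocol and SAP*

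**What the plan says.** Section 11.3 says that the PI's "study coordinator will perform all statistical analyses" and gives the reason: "This is in an effort to avoid any potential bias that could be created by the treating physician participating in the analysis". The same section chooses a paired t test and justifies landmarks and ratios by the variability of photographs.

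Section 11.2 states: "The endpoint is a comparative analysis of pre and post-treatment photographs". It adds: "Measurements and calculation will be performed based off of the portrait and profile images". Section 9.1 says that the efficacy assessment "will be done through comparative measurements taken on pre and post-treatment photographs". None of these sentences names who places the landmarks.

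The synopsis (section 1) and section 5 give the timing. Goode's ratio, the Z-angle and the vermilion ratio are documented from the baseline images before injection. The same measurements are recorded from the images taken after the post-OCR visit. Both sets of photographs are then assessed at the end of the study. The visit lists mention only the photography: "Subject undergo standard 2D digital portrait photography" in 8.1 and "Subject will undergo standardized 2D digital portrait photography" in 8.4.

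On design, section 5 says: "This is an open-label, prospective, postmarket study to assess the effect". The clinical hypotheses in the synopsis state that nasal tip projection, upper lip projection and vermilion height will increase. Section 9.1 says which direction of Z-angle change counts as more projection.

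**The concern.** The sponsor has seen that a person with an interest in the result could bias it, and has acted on that in 11.3. However, a paired t test leaves its operator little discretion. Discretion lies mainly in marking the tip-defining point, the nasion, the alar-facial groove, the profile tangent and the vermilion borders. A reader who knows that an image is post-treatment, and knows which direction is expected, can shift those marks without intending to.

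There is no control group, so a pre/post shift in reading has nothing to cancel against. It would enter both primary measures and the secondary measure, which are all the efficacy evidence the study produces.

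**Working it through.** **1. Search for masking.** The plan has four relevant controls:

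- 11.3, coordinator performs the statistics: controls who analyses, not what the reader knows.
- 9.2 and 11.3, ratios and landmarks: address camera distance, angle, lighting and photographic variability.
- Appendix A, photography procedure: addresses distance, head position and expression.
- 13.6, the only place where the word *blinded* occurs: concerns removing identifiers from copied records.

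No sentence codes images, randomises reading order, names an independent reader or conceals the visit. Three things could not be checked: the front pages, any material between sections 3 and 5, and the Appendix B diagram.

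**2. Both readings of the word *analysis* in 11.3.** Read narrowly, it means the statistics; the treating physician could then still measure. Read broadly, with 11.2 describing the endpoint itself as an analysis of photographs, it includes measurement. The coordinator then measures, with nothing concealing the visit. The gap remains either way.

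**3. Where the error could enter.** A baseline value fixed before injection cannot be adjusted toward a post-treatment image that does not yet exist. Expectation would then act mainly at follow-up. If both sets are re-measured at the end of the study, it can act on either. The plan does not say which values go into the t test.

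**4. Effect on the test.** Let e_pre and e_post be the mean reading errors at the two visits. Then:

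expected observed mean change = true mean change + (e_post − e_pre)

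A constant error cancels; a differential one does not.

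**5. Sensitivity, for illustration only.** The plan gives n = 20 without a derivation, so there is no figure to reproduce. It states no SD, alpha, sidedness or reader error; all four are assumed here. Let b = (e_post − e_pre) / SD of the change, with no true change. Then t has 19 df and noncentrality b√20.

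- Two-sided 0.05: critical t = 2.093, so the critical mean change is 2.093/√20 = 0.468 SD.
- One-sided 0.05, with the shift in the expected direction: critical t = 1.729, so 1.729/√20 = 0.387 SD.

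| b | b√20 | Rejection, two-sided | Rejection, one-sided |
|---|---|---|---|
| 0 | 0 | 0.050 | 0.050 |
| 0.10 | 0.447 | 0.071 | 0.11 |
| 0.25 | 1.118 | 0.186 | 0.29 |
| 0.50 | 2.236 | 0.56 | 0.70 |

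A simulation of 200,000 trials agreed for the two-sided case. These rates hold for any paired t test with n = 20. They say nothing about how large b is here, and cannot be converted to degrees or ratio units.

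**6. Possible price of masked reading.** Random-order reading gives up side-by-side landmark matching. At two-sided 0.05, a true change of 0.66 SD has 80% power. If the SD of the change rose by an assumed 5%, 10% or 20%, the standardised change would be 0.66/1.05 = 0.63, 0.66/1.10 = 0.60 or 0.66/1.20 = 0.55. Power would then be 76%, 72% or 65%.

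**7. Workload.** Appendix A requires three poses (frontal, left profile, right profile): 20 × 2 visits × 3 = 120 images. With the frontal view and one pre-named profile side only: 20 × 2 × 2 = 80.

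**The case against.** The strongest reply is that these are geometric measurements on named landmarks, not subjective grades. Section 9.1 defines the points for Goode's ratio, and the Z-angle uses a tangent and a levelled Frankfort plane. This stands in part: definition narrows the reader's discretion, perhaps most for the Z-angle, but someone still has to place each point.

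Second, baseline values documented before injection are protected from hindsight. This also stands in part, but it leaves the follow-up reading and the end-of-study assessment open.

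Third, masking would be imperfect, since faces or the treatment effect may be recognised, and random-order reading may add noise. Both are true. They argue for modest expectations, not for leaving the visit label in view.

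Fourth, open-label treatment is a legitimate choice for a small postmarket study. It is, and this point does not question it; open-label treatment does not prevent masked image reading.

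A reader might go further and infer that the treating physician will make the measurements. The text does not say so; it leaves the reader unnamed. A reader might also take the 0.186 or 0.56 above as this study's false-positive rate. The documents contain nothing that makes those offsets likely or unlikely, so that inference fails.

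**Conclusion.** The concern holds for the available text: the person measuring the photographs is not masked to visit, and the safeguard in 11.3 does not supply that masking on either reading. In a single-group pre/post comparison with a declared direction, differential reading error would pass straight into every efficacy endpoint, and the planned test could not detect it.

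Its size is unknown. The illustrative rates carry no weight on that question, and it would be wrong to conclude that the results will be biased. The conclusion assumes only that landmark placement leaves some discretion and that the parts not seen do not already provide masking. The change should be made because it is cheap and protects all the efficacy measures.

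**What to change.** Keep the sentence on who performs the statistics and add to 11.3 wording such as:

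> The measurements used in the paired t tests are made once, at the end of the study. Beforehand, a staff member who does not measure replaces file names and dates on the pre-treatment and 1-month images with random codes and holds the key. The coordinator, not the treating physician, measures the coded images in random order without knowledge of visit. The measurement file is locked before the key is linked. Measurements made during the study are not used in the efficacy analysis and are not shown to the reader before the lock.

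Amend the synopsis and section 5 to match. Changing 11.3 alone would leave a second, unmasked set of values, recorded at baseline and follow-up. The last sentence of the wording matters because section 10.2 has a clinical study coordinator oversee data completeness and database closure. If that is the same person as the reader, which the text does not settle, they could otherwise match coded images to values already seen.

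Cost: coding and one measurement pass of up to 120 existing images, or 80 if only the frontal view and one pre-named profile side are coded and measured. No visits, subjects or photographs are added, and the test is unchanged. It needs one staff member who does not measure; the documents give no staffing, so that availability is assumed. Baseline images may be read a second time.

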9.2 Secondary Variable Assessments

The secondary assessment is to evaluate the change in upper lip height by comparing the pre and post-injection ratio of upper lip vermilion height to lower lip vermilion height. This method was chosen because ratios eliminate any bias created by camera distance, angle, lighting, etc.

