Appendix A: Photography Standardization

Appendix B: Diagram of planned measurements

Appendix A: Photo SOP**Photography and Poses**

- Use the grid feature on any of these viewers to ensure the Frankfort Plane (imaginary line from tragus to infraorbital rim) is parallel to the floor
- Stand approximately 1.5m from patient with the camera in a portrait position. The location will be marked on the floor of the photography studio.
- Ensure the patient has a relaxed expression and that their lips are closed and eyes are open for each photo.
- Give instructions like, “Slowly move you’re your chin down” or “Slowly turn your nose to the left” to achieve the desired poses listed below

Standard Poses ([contact] m)

1. Frontal
 - a. Make sure the patient doesn’t have their chin high or low by checking the Frankfort Plane. For this view, the line on the viewfinder should extend from the right tragus, across both infraorbital rims and across the left tragus. This should be parallel to the floor
2. Left Profile
 - a. For this view, ensure the patient is not rotated to the left or right (hint: look at the eyebrows to see how much of the glabella you see).
2. Right Profile
 - a. For this view, ensure the patient is not rotated to the left or right (hint: look at the eyebrows to see how much of the glabella you see).

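### Goode's ratio corrects for camera distance but not for head turn: under assumed geometry, about 2–4 degrees of turn toward the camera looks like a 1 mm tip gain, and no rule matches the follow-up pose to baseline

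*Combined protocol and SAP*

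**What the plan says.** - **Analysis (11.3).** The section accepts that even standardised photographs vary and answers that "the decision was made to perform measurements based on facial landmarks and distance ratios". It then states: "Statistical analysis will be conducted using a paired" t test. It gives no alpha, sidedness or expected effect.
- **Primary measure (9.1).** For the numerator of Goode's ratio, "The nasal height is measured from the alar-facial groove to the tip-defining point". The denominator, nasal length, joins the nasion to that same tip point.
- **What ratios are said to do (9.2).** For the vermilion ratio, the secondary measure, the plan says that "ratios eliminate any bias created by camera distance, angle, lighting, etc".
- **Photography (Appendix A).** The photographer is told "Stand approximately 1.5m from patient with the camera in a portrait position", at a spot marked on the floor, with a viewfinder grid for the Frankfort plane. Left and right profiles are both taken. For each, the instruction is to "ensure the patient is not rotated to the left or right", with a cue based on the eyebrows and the visible glabella.
- **Follow-up.** Section 5 asks for follow-up photographs taken in the same manner as at baseline. Section 8.4 lists only the photography itself.
- **Size and design (5).** "The study will enroll and treat a total of 20 subjects", open-label, with no control group.

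The readable text does not say which profile is measured or whether the two are averaged. The content of Appendix B (measurements) is not readable in the copy reviewed, so no conclusion is drawn from its silence.

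**The concern.** Dividing one distance by another cancels anything that enlarges or shrinks both equally, such as standing closer. Head turn does not act equally on these two distances. The tip and nasion lie on the midline. The alar-facial groove lies roughly half an alar width to the side, on the side facing the camera. When the head turns, the groove slides relative to the tip in the image, so nasal height lengthens or shortens while nasal length hardly moves.

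Goode's ratio is one of the two measures in the primary objective. Pose differences between visits add to the variance of its change. If they ran consistently in one direction they would also shift its mean, and a single-arm before-and-after comparison could not tell that shift from a treatment effect.

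**Working it through.** The plan gives no figure to reproduce: no facial dimensions, rotation error, effect size or SD. Everything below is therefore assumed and shown over a range.

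**Inputs.** From the documents: the landmark definitions (9.1), n = 20 (5) and the paired t test (11.3). Assumed: nasal height h = 28 mm; nasal length L = 50 mm; groove y = 12–19 mm off midline; dorsum a = 20–34 degrees from vertical; groove-to-tip line horizontal; a 1 mm forward tip gain as the benchmark; a two-sided 5% test.

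**Step 1: effect of yaw.** For a turn of t toward the camera (parallel projection):

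- Height: H = h·cos t + y·sin t
- Length: L' = L·√(cos²a + sin²a·cos²t)

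At y = 17 mm, a = 34°, t = 3°: H = 28.85 mm and L' = 49.98 mm. The ratio goes from 28/50 = 0.560 to 0.577. Changes by angle:

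| Turn | 1° | 2° | 3° |
|---|---|---|---|
| Toward camera | +0.0059 | +0.0116 | +0.0173 |
| Away | −0.0060 | −0.0121 | −0.0183 |

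The lateral landmark causes this. At 3°, y·sin t = 17 × 0.0523 = 0.89 mm. With y = 0 the height would change by only 28 × (1 − cos 3°) = 0.04 mm.

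**Step 2: effect of a true 1 mm gain.** The tip is an endpoint of both distances, so moving it forward also lengthens the nose: (h + 1)/√((L·sin a + 1)² + (L·cos a)²).

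- a = 34°: 29/50.57 = 0.5735, a gain of 0.0135
- a = 20°: 29/50.35 = 0.5760, a gain of 0.0160

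**Step 3: the turn that mimics 1 mm.** Solve H/L' from step 1 for the value in step 2:

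| Groove off midline | 12 mm | 15 mm | 17 mm | 19 mm |
|---|---|---|---|---|
| a = 34° | 3.4° | 2.7° | 2.3° | 2.1° |
| a = 20° | 4.1° | 3.2° | 2.8° | 2.5° |
| Gain taken as (h + 1)/L, length held at 50 mm | 5.2° | 4.0° | 3.5° | 3.1° |

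The first two rows give about 2–4 degrees. The third ignores the lengthening in step 2 and is an outer bound.

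**Step 4: precision.** Take 0.006 per degree, true-change SD 0.015, mean change 0.0135 and per-photograph yaw SD of s degrees.

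- One profile per visit: SD = √(0.015² + 2·(0.006s)²)
- Mean of two profiles with independent errors: SD = √(0.015² + (0.006s)²)

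Power comes from the noncentral t distribution with 19 df and noncentrality 0.0135/(SD/√20):

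| s | SD, one profile | Power | SD, two averaged | Power |
|---|---|---|---|---|
| 0° | 0.0150 | 97% | 0.0150 | 97% |
| 1° | 0.0172 | 91% | 0.0162 | 94% |
| 2° | 0.0226 | 72% | 0.0192 | 85% |
| 3° | 0.0295 | 49% | 0.0234 | 69% |

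Other assumptions change this greatly. With mean change 0.020, one-profile power at s = 2° is 96%. With true-change SD 0.025 and mean 0.0135, power is only 63% before any yaw error.

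**Step 5: a consistent shift, if there were one.** A 1° difference in mean yaw between visits moves apparent height by 17 × sin 1° = 0.30 mm. With an assumed paired SD of 1–2 mm, the noncentrality is 0.30/(SD/√20), about 1.3 to 0.7. The chance of a false positive in the hoped-for direction rises from 2.5% to about 24% or 9% respectively.

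**The case against.** **The plan does control rotation.** This stands. Appendix A gives a direct instruction, a visual cue, a grid, a marked position and two profiles, and section 5 asks for like-for-like follow-up photographs. A reader might infer that rotation is uncontrolled; the documents do not support that. What the readable text lacks is narrower: a comparison of the follow-up pose with baseline and a rule for retaking.

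**Section 11.3 does not claim that ratios cancel rotation.** Also correct. It says only that landmarks and ratios were chosen because photographs vary. The statement about camera angle is in 9.2 and concerns the vermilion ratio. It would be over-reading to attribute it to Goode's ratio.

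**The degree figure is not a property of this trial.** Agreed. It is tempting to state one tight value as fact, but it depends on the offset and the dorsum angle, neither of which is in the documents. It applies only to a turn toward the camera, and the 1 mm benchmark is not the plan's.

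**Random yaw does not create an effect.** Right. Errors in both directions roughly cancel in the mean and cost precision. A reader might infer that the primary result will be biased upward, but no cause of a consistent between-visit turn under the same photography procedure is shown. Step 5 is conditional on such a shift.

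**Two profiles may already reduce the noise.** They do if averaged and if their errors are independent, as step 4 shows. The readable text does not commit to averaging, and averaging does not help when both views at one visit are turned toward the camera.

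**Conclusion.** The point holds in limited form. By the plan's own landmark definitions, Goode's ratio is sensitive to yaw to first order, and using a ratio does not protect it. Under the assumed geometry, 2–4 degrees toward the camera is worth about 1 mm of apparent tip projection, and the opposite turn an apparent loss. The likely consequence is lost precision in a 20-subject study. Its size cannot be fixed from the documents, and the power figures illustrate one scenario. Bias is possible only with a systematic pose difference between visits, which this design could not separate from treatment effect. The point concerns Goode's ratio in the profile view. It does not extend to the Z-angle, which is not a distance ratio. It is worth correcting because the measure is primary and the correction is cheap; it does not invalidate the study.

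**What to change.** 1. **Appendix A and 8.4.** When taking each Visit 3 profile, overlay that subject's baseline image from the same side. Match head rotation and framing, and retake before the subject leaves if they visibly differ.
2. **Yaw check.** Support the visual match with a yaw-sensitive measure, such as the horizontal tragus-to-nasion distance scaled by a vertical distance that neither yaw nor treatment changes. Set its tolerance from repeat photographs, not as a fixed percentage. A 1.5% cut-off scaled by ear height, for example, would be too fine: on an ear assumed to be 60–65 mm tall, a 1 mm landmark error alone is 1/65 to 1/60, or 1.5–1.7%.
3. **Section 11.3.** State that ratios correct for camera distance only and not for head rotation. Specify that the analysed Goode's ratio is the mean of the left and right profile values at each visit. Both views are already photographed.

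Cost: protocol and photography wording, a small set of repeat photographs to set the tolerance, a second profile measurement per visit, and a few minutes with occasional retakes at a visit already scheduled. No extra visits.

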1 PROTOCOL SYNOPSIS**TITLE:**

Premaxillary injection for perioral rejuvenation and upper lip enhancement

INDICATION:

Premaxillary injection performed via cannula technique for perioral rejuvenation

SAMPLE SIZE:

20

NUMBER OF CENTERS:

One

PURPOSE:

To determine if subjects who receive premaxillary injection demonstrate an increase in nasal tip projection and an associated increase in upper lip projection, and vermillion height.

SUBJECTION SELECTION:

A total of 20 subjects who display signs of perioral aging or poor upper lip projection

PROCEDURE:

This is an open-label, prospective, post market study to assess the effect of premaxillary hyaluronic acid filler injection on nasal tip projection and upper lip position.

The study will enroll and treat a total of 20 subjects who are filler naïve and do not have any history of rhinoplasty, recent upper lip augmentation <12 months, lip lift or other surgical procedures involving the upper lip, chin augmentation and orthognathic surgery. Patients in study are restricted from perioral neurotoxin, peri oral ablative resurfacing, facial cosmetic surgery, all subdermal directed aesthetic treatments or filler treatment other that which is dictated in the protocol during the course of the study.

Subjects, who fulfill all eligibility criteria, will undergo pre-treatment standardized 2D portrait photography. From the profile image, baseline nasal projection measurements will be documented according to Goode's ratio. Additionally, baseline upper lip position will recorded by measuring the Z-angle, which is the intersection of the Frankfort horizontal line and the profile line as described by Merrifield. From the straight portrait image, the ratio of the upper lip vermillion height to the lower lip vermillion height will be documented. Subjects will then be injected with a maximum of 4 syringes of Restylane® Defyne to treat their premaxillary space per the discretion of the Principal Investigator (PI). If optimal correction result (OCR) has not been achieved additional touch-up injections of Restylane® Defyne may be injected 2 weeks post treatment visit to achieve OCR as per PI discretion.

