Post OCR visits will be performed at 4 weeks following premaxillary injections. Subjects will be followed to assess any treatment-related adverse events (such as pain, nodules, swelling, redness, bruising, tenderness, itching, and headache) as well as pigmentation changes and/or keloid formation. Each subject will then be photographed with standardized photographs in a similar fashion as pre-treatment and the same measurements will be recorded.

Upon study culmination, pre-treatment and 1-month post OCR photographs will be assessed. Each patient will be evaluated to determine if nasal tip projection was increased causing an increase in upper lip projection. Additionally, the vermilion ratios will be compared to evaluate for change in upper lip vermilion height.

STUDY DURATION:

Each subject will undergo screening assessment of eligibility criteria, pre-treatment photography, and if eligible for treatment, injections of the premaxillary area. All enrolled subjects will be followed up to 1-month post OCR visit to evaluate the injections effect on nasal tip projection and upper lip projection.

OBJECTIVES:

The Primary Objective of this study is to determine the increase in nasal tip projection (measured by Goode's ratio) and the increase in upper lip projection (measured by the Z-angle) following perioral rejuvenation with premaxillary hyaluronic acid filler injections.

The Secondary Objective of this study is to assess the change in upper lip height by comparing the pre and post-treatment injection ratio of upper lip vermilion height to lower lip vermilion height.

CLINICAL HYPOTHESES:

Subjects who are treated with premaxillary injection will demonstrate an increase in nasal tip projection and have an associated increase in upper lip projection. Additionally, the upper lip will demonstrate an increase in upper lip vermilion height. As a result, the single injection site will address multiple factors that contribute to perioral aging.

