3 STUDY OBJECTIVES

The Primary Objective of this study is to determine the increase in nasal tip projection (measured by Goode's ratio) and the increase in upper lip projection (measured by the Z-angle) following perioral rejuvenation with premaxillary hyaluronic acid filler injections.

The Secondary Objective of this study is to assess the change in upper lip height by comparing the pre and post-treatment injection ratio of upper lip vermilion height to lower lip vermilion height.

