6 SUBJECT SELECTION

A total of 20 subjects.

All Subjects must comply with the following inclusion and exclusion criteria:

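### The paired t test answers the two mean increases in the primary objective, but it cannot show that the lip increase is associated with, or caused by, the tip increase

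*Combined protocol and SAP*

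**What the plan says.** The documents describe the relation between nasal tip and upper lip in three ways.

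- **Two increases.** The primary objective (Section 3, repeated in the synopsis) is to "determine the increase in nasal tip projection (measured by Goode's ratio) and the increase in upper lip projection (measured by the Z-angle"). It says nothing about a link between them.
- **An associated increase.** The synopsis purpose is to learn whether subjects "demonstrate an increase in nasal tip projection and an associated increase in upper lip projection, and vermillion height". The clinical hypothesis is that "Subjects who are treated with premaxillary injection will demonstrate an increase in nasal tip projection and have an associated increase in upper lip projection".
- **A caused increase.** Section 5, and the synopsis in the same words, adds: "Each patient will be evaluated to determine if nasal tip projection was increased causing an increase in upper lip projection". No method or criterion for this evaluation is given.

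On analysis, Section 11.3 says only: "Statistical analysis will be conducted using a paired" *t* test. It does not list the measures to be tested; one test per measure is the natural reading. No correlation, regression or concordance rule appears anywhere. Section 9.1 fixes the direction of the lip measure: "A change in the angle to a more acute value on postoperative photographs would indicate an increase in upper lip projection".

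**The concern.** A paired t test asks whether the mean change in one measure differs from zero. It uses no information on whether the subjects with larger tip gains are also those with larger lip gains. The purpose, the hypothesis and the causal sentence all go beyond two mean changes, and the plan has no analysis that follows them there.

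The risk lies in how the results are reported. Two significant t tests could be written up as confirming an associated, or even caused, lip increase when the two changes are unrelated across subjects or run in opposite directions.

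**Working it through.** **1. What the test uses.** Let d be a subject's change in Goode's ratio and e the change in Z-angle. The two statistics are t = mean(d) / (SD(d)/√n) and t = mean(e) / (SD(e)/√n). Reassigning the e values among subjects alters neither mean nor SD, so both t values stay the same while the correlation of d with e can take a quite different value. This needs no assumption about effect size.

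**2. Inputs.** From the documents: n = 20 (Section 6, "A total of 20 subjects"). Significance level, sidedness, power, effect size and SD of change are not stated, so the figure of 20 cannot be reproduced. Assumed here: two-sided 0.05, bivariate normal changes, and the same standardised mean change on each measure (0.66, 0.8 or 1.0 SD). The value 0.66 is where one paired t test at n = 20 has 80% power. Both changes are oriented so that positive means more projection. In raw units the Z-angle sign reverses, so +0.8 below corresponds to −0.8 between Goode's ratio and Z-angle.

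**3. Power of one test.** Noncentral t, 19 df, noncentrality δ√20:

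- δ = 0.66: 0.66 × 4.472 = 2.95, power 79.9%
- δ = 0.8: 0.8 × 4.472 = 3.58, power 92.4%
- δ = 1.0: 1.0 × 4.472 = 4.47, power 98.9%

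These do not depend on the correlation.

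**4. Both tests significant.** If each test has power p, the joint probability must lie between 2p − 1 and p whatever the correlation, and is p² for uncorrelated normal changes. Simulation (100,000 trials per setting) fills in the rest:

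| Mean change | 2p − 1 to p | p² | ρ = −0.8 | ρ = 0 | ρ = +0.8 |
|---|---|---|---|---|---|
| 0.66 SD | 59.9% to 79.9% | 63.9% | 60% | 64% | 73% |
| 0.8 SD | 84.8% to 92.4% | 85.4% | 85% | 85% | 89% |
| 1.0 SD | 97.7% to 98.9% | 97.7% | 98% | 98% | 98% |

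The spread is 13 points at 0.66 SD (73 − 60), 4 points at 0.8 SD and none at 1.0 SD. Joint significance therefore says little about the association. For contrast, a test of the correlation itself at 0.8 SD (40,000 trials) rejects in 99.6%, 5.1% and 99.6% of trials at the same three values.

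**5. What a correlation can deliver at n = 20.** On the Fisher z scale the standard error is 1/√17 = 0.2425. For an observed |r| of 0.5, atanh(0.5) = 0.549, and 0.549 ± 1.96 × 0.2425 = 0.074 to 1.025, which back-transforms to 0.07 to 0.77. In the hypothesised direction that is −0.77 to −0.07. As a two-sided test, significance needs |r| of at least 0.444. Power, Φ(atanh|r| × √17 − 1.96), is 25%, 42%, 62% and 82% at true |r| of 0.3, 0.4, 0.5 and 0.6.

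**The case against.** The strongest reply is that *associated* means only *accompanying*. Section 9.1 frames the primary assessment as the injection's effect on tip and lip projection, through before-and-after measurements. On that reading two significant t tests largely answer the hypothesis. The Background may seem to say that this trial applies a known tip–lip correlation, but that sentence describes earlier work in a small group of patients. It also presents the rhinoplasty result as a significant lip increase seen as the tip was projected, which fits co-occurrence as well as correlation.

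Much of this stands. A reader might infer that the trial's main question goes untested; the documents do not support that, because the stated primary objective is the two mean increases and the t test addresses them. What the reply does not cover is the sentence in Section 5 and the synopsis about the tip increase causing the lip increase, which co-occurrence cannot satisfy. If co-occurrence is all that is meant, the wording should say so.

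A second reply is that 20 subjects are too few for a correlation. As a hurdle for using the word *associated*, a significance test would indeed often deny a real moderate link (62% power at |r| = 0.5). That argues for estimation with an interval; it does not argue for leaving the association unexamined.

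**Conclusion.** The concern holds for the association and causal wording only. The planned test answers the primary objective. It cannot support the claim that the lip increase is associated with, or caused by, the tip increase.

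That the test ignores covariation is an algebraic fact. The percentages rest on assumed effect sizes, normality and a 5% two-sided level, none of which the documents give. The insensitivity to correlation is least marked at 0.66 SD, where the joint result moves from 60% to 73%, and close to complete at 0.8 SD and above.

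A reader might also infer that adding a correlation would establish cause. It would not: there is one arm, one injection may move both structures directly, and both measures can come from the same profile photograph, so shared pose error can contribute to the correlation.

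**What to change.** **Section 11.3.** Add text to this effect: *The within-subject change in Z-angle will be related to the within-subject change in Goode's ratio by a correlation coefficient and a regression slope, each with a 95% confidence interval, and shown in a scatter plot. This is estimation; no significance threshold applies. A negative sign is the hypothesised direction, because a more acute Z-angle means more lip projection, and only an association in that direction supports the hypothesis. Both measures may share photographic pose error.*

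**Section 5 and synopsis.** Replace the sentence on the tip increase causing the lip increase with a reference to this association analysis.

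**Alternative.** If only co-occurrence is meant, reword the purpose and hypothesis as separate mean increases. The causal sentence then needs the same correction.

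**Cost.** A few sentences and one extra estimate from photographs already planned at screening and at the one-month visit. The downside is a wide interval at n = 20, so the association may not be supported.
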